attitudes regarding dialysis and kidney transplantation. The questionnaire assesses three areas of interest; (1) demographic characteristics and the availability of social and emotional support; (2) self-reported health, quality of life, and the specific impact of kidney disease and its treatment; and (3) patient views of kidney transplantation, including self-reported listing status and perceived bias in transplantation allocation. (4) who patients talk to in the hemodialysis clinic, what they talk about and how often. Many of the items included in the DPTQ have been validated in hemodialysis and transplant populations⁸⁻¹⁵ including quality of life measures and independent predictors of mortality. Previous research has speculated that the social networks that patients form in the hemodialysis clinic may influence attitudes and behaviors towards transplant and may be amenable to social network interventions. Social network behavioral interventions in other fields¹⁶⁻²¹ have found that it may be better to target dense (clustered) networks than diffuse networks. As diffuse networks function as discussion networks and can be more effective in changing behavior than diffuse networks which function as advice networks and are better at spreading novel information through a central person¹⁹⁻²¹. Once patients social networks have been mapped, we will assign every HD clinic shift to one of the two targeting strategies based on social network attributes for the COACH intervention. We will measure the spread of information, attitudes, and behaviors by comparing the targeted patients to those that they refer, as well as the other patients on their shift. The COACH was specifically designed to educate patients on kidney disease and communication skills to approach other people about potential donation.

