Survey Instrument: The *Dialysis Patient Transplant Questionnaire* (DPTQ) includes a mix of 49 questions, single measures, and scales previously validated in HD and transplant populations and items developed to address the co-investigators' specific research interests (see appendix). The DPTQ has demonstrated construct validity in previous studies^{1,4,11,12}. It includes 17 items on communication confidence developed specifically to evaluate the COACH program and rated along a scale from 0 to 100 (Cronbach's alpha = .90); summed to create a composite confidence score. In addition, there are 12 true/false items on transplant knowledge items; correctly answered items are summed to create a composite knowledge score. The questionnaire will also include questions regarding medical conditions which may preclude the patient from transplantation. Clinic staff will also participate in a modified version of the survey to assess their attitudes towards HD^{48,49} and kidney transplantation, during Year 2.

Participant HD Seating and Observed Interaction Log: Patient seating assignments will be recorded, as well as, the staff observed social interaction log, which documents the frequency, duration, and nature of observed patient-patient interactions (appendix).

Clinical Data: Upon consent, routine HD laboratory and clinical data (including co-morbid conditions, e.g. diabetes, congestive heart failure, cardiovascular disease, chronic obstructive pulmonary disease, and malignancy, which will be reconciled with survey data) will be extracted from the DARWIN database by the DCI Information Technology Department. Data will be downloaded, cleaned, merged, and submitted for preliminary analysis. Patient's steps to transplantation (Table 2)^{1,2} will be recorded and listing status will be verified with the patient transplant center or centers (**AIM 2**).

Analytic Plan AIM1: To test **H1**, we will create nodal network graphs (Figure 1, for example) using data collected from the patient and staff surveys, and clinical observations. We will characterize and compare the structure of the patient HD clinic networks by gender and race. We will assign demographic, survey, and clinical data abstracted from the EMR to each node in the network.

Primary outcome: Differences in clustering and centrality by gender and race (**H1**)

Independent Variables: Sex and Race

Covariates: Age, Marital Status, HD vintage, insurance, HD Clinic, and HD shift

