Analytic Plan AIM 2: To test **H2**, we will use the network information from Aim 1 to analyze correlation of knowledge, attitudes, and behaviors between members of the network (transplant discussions, living donor recruitment, and step in kidney transplant process) from the surveys and the EMR.

Primary Outcome: Correlation of 1) attitudes about transplantation and 2) step in transplant process

Independent Variables: Clustering coefficient and attributes of alters

Covariates: Age, Marital Status, HD vintage, insurance, transplant eligibility, HD clinic, network attributes

Analysis: We will examine how knowledge, attitudes, and completion of steps differ by network attributes. These differences will then be validated by using logistic regression modeling to predict patient's attitudes towards transplantation and step in the transplant work-up using demographic and survey variables. We will then add network attributes and quantify the improvement in the prediction model using tests for goodness of fit. To further validate the model we will perform an Exponential Random Graph Model (ERGM) with temporal attributes⁵³ in which the patients current transplant step is a function of patients baseline data and network attribute as well as their alters' baseline step, current step, and network attributes.

Limitations: We have previously found that patients are often incorrect about their listing status⁴, thus we will confirm the transplant status by contacting the listing institution. Using the steps completed will allow for the analysis of patients that are highly motivated who complete all their work-up but are discovered to have an absolute contraindication to transplantation. Since AIM 1 and 2 are observational, we will be unable to determine whether patients form small networks with like-minded individuals or whether over time everyone in a small network will reach a common belief through spread of information and behaviors⁵⁴. To test the spread of information and behaviors, in **AIM 3**, we will use a network targeted intervention.

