patient selected by clustering, will have a clustering coefficient greater than 1 SD from the mean and centrality 1 SD less than a mean. In our previous study, there was no correlation between clustering and centrality ($r=0.024$, $p=0.875$). The research and clinical staff will be blinded to whether the patient was chosen to participate in COACH because of clustering or centrality. Patients will be excluded if they are ineligible for a kidney transplant, had a previous kidney transplant, or have an active living donor.

Assignment of Intervention groups: The intervention assignment will be alternated between MWF and TTS (Table 3) to avoid patient differences between those respective days (for example patients on MWF may have been on dialysis longer while patients on TTS may be more likely to work)⁵⁵.

Retention/Attrition: **AIM3** will be carried out over the course of a year with a possible drop-out rate of 5% (Death and Transfer). If a patient transfers, the patient will be contacted via phone to do a follow-up survey.

Participant Remuneration: All patients will receive \$10 for the initial survey (Wave 1), and Wave 2 survey, \$10 for the 3 month follow-up (Wave 3), and \$10 for Wave 4. Patients will not receive remuneration for participating in the COACH education but will be able to keep the handouts and reading materials.

Data Collection (AIM 3)

Education Intervention: COACH is a behavioral communication intervention designed specifically for ESRD patients pursuing kidney transplantation. The COACH program (appendix) consists of four modules: 1) Kidney transplant options, 2) Discussing your transplant options, 3) Requesting living donation, and 4) Maintaining positive relationships. The content and teaching strategies were guided by the concepts of social cognitive theory as well as principles of adult learning and communication skill acquisition^{31,56,57}. A study coordinator will conduct the intervention in four, face to face, one hour sessions in the HD clinic. Patients will receive the a handbook and video for the COACH intervention.

Shift	Clinic 1		Clinic 2	
	MWF1	TTS1	MWF2	TTS2
1st 5am-9am	Cluster	Central	Central	Cluster
2nd 9am-1pm	Cluster	Central	Central	Cluster
3rd 1pm-5pm	Cluster	Central	Central	Cluster

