Staggered Surveys: We propose a pre-post design to assess the impact of the COACH education on patients' transplant-related knowledge and behaviors. Before administering the COACH education, we will survey targeted patients to assess changes in knowledge and behaviors towards transplant from the baseline survey. As another measure of the impact of the COACH intervention, patients not receiving the intervention will serve as controls and will be surveyed along with those receiving the intervention; we will then assess within and between group differences in transplant-related knowledge and behaviors. To assess the dissemination of information contained in the COACH intervention, all patients will be surveyed at 3-months post-intervention. The follow-up surveys will determine the sources of these changes (eg. self-reading after the survey, the COACH intervention, or discussing with other patients). Finally, during Year 4, one year post-intervention, a final survey will be administered to the all the patients in both clinics to assess retention of information and change in attitudes and behaviors of those who participated in COACH and the spread of information and behaviors to the patients who were not targeted.

Clinical Data: In addition to the survey data, we will collect patient transplant listing status, living donor evaluations from participants' respective transplant centers.

Analytic plan AIM3: To test **H3** we will assess the successful spread of the intervention by evaluating the difference in the primary outcome of completion of steps toward transplantation between patients being exposed via the most clustered (Cluster) members versus the most central (Central). We will use repeated surveys to measure our secondary outcomes include change in knowledge, attitudes, behaviors of the patients either directly exposed to the intervention or those who were exposed indirectly through the social network.

Primary Outcomes: 1) Differences in patient knowledge, 2) Differences in transplant steps completed

Secondary Outcomes: 1) Completion of transplant work-up, 2) Asking for a living donor

Independent Variables: Intervention assignment to Cluster or Central

Covariates: Age, Marital Status, insurance, transplant eligibility, HD shift, HD Clinic, network attributes

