Exposure: While only two patients per shift will receive the COACH intervention, all patients regardless of participation in the COACH education will be analyzed as exposed to the intervention via social spread. This will result in two groups for the primary analysis Cluster (MWF1 Cluster + TTS2 Cluster) and Central (MWF2 Central + TTS1 Central)

Analysis: To measure global changes, we will use a t-test to test changes in knowledge and changes in completion of steps between Cluster and Central. Individual level transfer of information will be analyzed with a

Markov chain Monte Carlo accept-reject procedure in the chain⁵⁸. We will examine the correlation in changes of a patient's(ego) knowledge with his or her first degree alter and measure the decay in correlation as the degree of the alter increases. We will also examine the ego's distance (how many links the patients are from each other) from the alter receiving the intervention. In addition, we will use Gaussian Conditional Random Fields (GCRF) methods to model a patient's stage in the transplant process by taking into account various factors such as personal demographics, social influence of alters, and global trends of HD shift and clinic⁵⁹. We will examine the characteristics of the patients disseminate and receive information. The data directly measuring the spread of information, influence, and behavior within the network from this experiment will be used to validate and strengthen the social network model developed in AIM1 and AIM2.

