Limitations: If the targeted patient refuses to participate, we will select another two transplant eligible patients to participate in the intervention based on their clustering and centrality. The network attributes of the patients if they refuse to participate will be analyzed and can inform AIMS 1 and 2 as well as recruitment strategies for future studies. In the unlikely event no patients on the shift participate in the COACH education, they will be analyzed as intention to treat. Since we are measuring change in knowledge using repeated surveys we are at risk for a learning effect⁶⁰. For this reason on the repeated survey questionnaires, we will also assess where the new knowledge came from patient interactions or self-reading after the survey. Given the focus of the proposed research on urban and suburban locales, future research is indicated to see if this social network mapping and intervention can also be used in rural settings, especially since recent studies shown many patients in rural southeast are disadvantaged regarding transplantation⁶¹.

Sample size and power AIM3: Using the data from our previous HD clinic social network study, we expect the patients in the Clustering targeted intervention to complete at least 2 more steps in the transplant work-up than those in the Centrality intervention (7, SD 1.5 vs 5, SD 1.7, p=0.03). The observed effect size was 1.06 or a difference of 2 steps. We estimate at least 10 patients per shift will be exposed to the intervention either directly through participation in the intervention or indirectly through information/behavior spread through the social network. Both clinics have 6 shifts, and we would have 60 patients assigned to each intervention condition. Based on a two tailed t-test, a total sample of 30 (15 in each treatment arm) would yield 80% power at significance level $\alpha = 0.05$ to detect a difference of 2 steps. With 120 patients (60 patients in each treatment arm) we will be powered to detect a difference of 1 step. The COACH intervention produced a change in knowledge³ with an effect size of 1.2, thus if we expose 90 patients (45 in each arm) to the intervention, we will have the power to detect at least half that effect.

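### The Aim 3 covariate list omits HD vintage and leaves HD shift undefined, and no Cluster-Central model is said to use the list, so a dialysis-day gap in vintage that differs between the two clinics stays in the comparison

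*SAP*

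**What the plan says.** The Aim 3 analytic plan (SAP 3.C) names assignment to Cluster or Central as the independent variable and then gives "Covariates: Age, Marital Status, insurance, transplant eligibility, HD shift, HD Clinic, network attributes". The corresponding lists for the other aims both contain vintage:

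- Aim 1: "Covariates: Age, Marital Status, HD vintage, insurance, HD Clinic, and HD shift"
- Aim 2: "Covariates: Age, Marital Status, HD vintage, insurance, transplant eligibility, HD clinic, network attributes"

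No reason is given for the difference.

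Under Assignment of Intervention groups the SAP says "The intervention assignment will be alternated between MWF and TTS (Table 3) to avoid patient differences between those respective days", and its example of such differences is that "patients on MWF may have been on dialysis longer while patients on TTS may be more likely to work". In Table 3, Clinic 1 has Cluster on MWF and Central on TTS, and Clinic 2 has the reverse.

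The Aim 3 Analysis paragraph compares changes in knowledge and in steps between the arms by t-test. It does not say which model uses the covariates.

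Shift is used in more than one sense. Protocol section 4 says "we will assign every HD clinic shift to one of the two targeting strategies", and the SAP sample size section says "Both clinics have 6 shifts", which makes 12 assigned units. The rows of Table 3, headed Shift, are three time slots, and the Setting section speaks of 3 shifts on each set of days.

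**The concern.** Aim 3 is the only aim in which the comparison groups are formed by dialysis day, and it is the only one whose list leaves out the patient characteristic that the SAP expects to vary by day. If vintage predicts progress through the steps and is not balanced between arms, part of the Cluster-Central difference would reflect who dialyses when.

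The list also includes HD shift without saying what it is. Whole clinic-shifts are assigned to arms, so arm is constant within each of the 12. An analyst who entered those 12 as fixed levels would find arm aliased with them, and any arm coefficient that the software printed would depend on which column it had dropped.

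**Working it through.** **Inputs.** From the SAP: the Table 3 layout (2 clinics x 2 day sets x 3 slots = 12 clinic-shifts), 10 patients per shift, 60 per arm, effect size 1.06 for 2 steps, two-sided alpha 0.05. Assumed, because the documents give no figures: the size of the day gap in vintage, the slope of step change on vintage, and their correlation.

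**The plan's own figure.** At d = 1.06, 15 per arm gives 80.0% power by two-sample t-test, as stated. For 1 step, d = 0.53 and 60 per arm gives 82%. The SD implied by the stated effect size is 2/1.06 = 1.89; the printed SDs of 1.5 and 1.7 pool to 1.60. I use 1.89. The sample size does not depend on the present point.

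**What the reversal balances.** Let M1, T1, M2, T2 be mean vintage on MWF and TTS in clinics 1 and 2, with equal shift sizes. Cluster is MWF1 and TTS2; Central is MWF2 and TTS1. Then

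Cluster - Central = (M1 + T2)/2 - (M2 + T1)/2 = ½[(M1 - T1) - (M2 - T2)].

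- Equal gaps in both clinics: 0. The reversal works.
- Gap of 0.5 SD in one clinic and 0 in the other: ½(0.5 - 0) = 0.25 SD.
- At an assumed slope of 0.3 to 0.6 step per SD: 0.25 x 0.3 = 0.08 and 0.25 x 0.6 = 0.15 step.

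**Can clinic and day terms remove it?** The rank of the design matrix for Table 3, without and then with arm:

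| Terms besides the intercept | Rank without arm | Rank with arm | Arm estimable |
|---|---|---|---|
| Clinic + day | 3 | 4 | yes |
| Clinic x day | 4 | 4 | no |
| Clinic + 3 time slots | 4 | 5 | yes |
| Clinic + day + 3 time slots | 5 | 6 | yes |
| Clinic + 6 day-slots | 7 | 8 | yes |
| Clinic + 12 clinic-shifts | 12 | 12 | no |

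The second row shows that arm is the clinic-by-day interaction. Main effects of clinic and day therefore cannot remove a gap that differs between clinics; patient-level vintage can remove the part that vintage carries. In the estimable 3-slot, 6-day-slot and clinic-plus-day codings, arm is uncorrelated with the other terms (variance inflation 1.0).

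**Precision.** If vintage correlates 0.3 with step change (assumed), the residual SD is 1.89 x √(1 - 0.09) = 1.80, and power for 1 step at 60 per arm rises from 82% to 85%. Both figures treat patients as independent.

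**The case against.** The strongest reply is that the SAP saw the day problem and met it by design. Each arm has three MWF and three TTS shifts, and three shifts in each clinic, so a common day effect drops out. That stands. What does not follow is that the design covers a gap of different size in each clinic. The Setting section describes very different populations: 94% African American with median income 28,363 US dollars, against 43% White with 82,406. Equal gaps are possible, but they are an assumption. The documents do not report an unequal gap either.

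A second reply is that the stated test is an unadjusted t-test on changes, so the list does no harm to it. That is correct. Because the outcome is change, vintage matters only so far as it predicts change. The gap is that a list is given with no model to use it.

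Three stronger readings are tempting, and the documents support none of them.

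- **That the planned arm effect cannot be estimated.** This needs HD shift entered as 12 clinic-specific fixed levels. The list names HD Clinic separately, which would be redundant under that coding, and the Table 3 rows point to time slots. A random shift term would also leave arm estimable.
- **That the model with "global trends of HD shift and clinic" has the same fault.** The SAP describes it as a model of a patient's stage and states neither an arm term in it nor a fixed trend for each of 12 shifts.
- **That employment, the other day difference the SAP mentions, should be added.** The documents do not show that it is collected.

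**Conclusion.** The omission of vintage is real under any coding of shift, and unexplained. The reversal between clinics protects against a common day difference but not against a clinic-specific one, which is fully confounded with arm. The likely size is modest: 0.25 SD of vintage and 0.08 to 0.15 step in the example, against the 1 to 2 steps the trial is powered for. Those figures rest on an assumed gap, assumed slopes and equal shift sizes; with unequal shift sizes even a common gap would not cancel exactly. Adjusting for vintage cannot remove other clinic-by-day differences.

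The ambiguity of HD shift calls for a definition. It is not a demonstrated failure of the analysis: only one of the three fixed-effect codings of shift makes arm inestimable, and the SAP does not say that it will use that one. The point is worth correcting because the correction is cheap, not because the stated t-test is invalidated by it.

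**What to change.** In the Aim 3 analytic plan:

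1. Add HD vintage to the covariate list, as in Aims 1 and 2.
2. State that, besides the t-test, the Cluster-Central comparison of changes will be estimated in a regression using that list.
3. Replace HD shift by dialysis day (MWF/TTS) and time slot (1st/2nd/3rd) as fixed factors alongside clinic. Let the 12 clinic-shifts enter only as a random intercept, never as fixed effects.

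With clinic, day, slot and arm fixed (rank 6), 12 - 6 = 6 degrees of freedom remain at shift level, so the plan should also say how degrees of freedom are set.

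The cost is SAP wording and one additional model. Vintage is already a covariate in Aims 1 and 2, so no new data and no more patients are needed.

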AIM3: Compare and contrast the diffusion of knowledge, attitudes, and behaviors regarding transplantation through HD social networks by targeting either the most central or the most clustered members of the network to disseminate a transplant education intervention. **H3:** Targeting patients with high clustering coefficients will be the most effective method for the spread of knowledge and favorable attitudes toward transplantation, and completing steps toward transplantation as compared to targeting by centrality.

Rationale: Previous studies have shown that barriers to transplantation tend to be less about information but rather behaviors related to completing the transplant steps^{1,2,4,13}, thus dense social networks are likely to be more effective in changing behavior and participating in a social network than diffuse networks, which are more effective at spreading novel information³²⁻³⁴.

Patient Recruitment, Eligibility, and Retention AIM 3: One year after the initial survey, we will use a targeted network intervention to measure the spread of information, attitudes, and behaviors. We will target transplant eligible patients based on their clustering coefficient or their betweenness centrality to participate in the COACH education using data collected in AIMS 1 and 2.

Recruitment Goals: Based on previous research^{1,4}, we anticipate approximately half the patients would be eligible for a kidney transplant but not on the list. If 250 patients participate in **AIM 1 and 2**, then at least 125, or approximately 10 patients per shift will be eligible for the intervention. The intervention will target either the two most central transplant eligible patients or the two most clustered patients to participate in the COACH education. As this is a social network intervention, although we are targeting only two patients per shift, all the patients on that shift are considered exposed to the COACH education. To prevent selecting a patient that is both relatively central and clustered, the patients selected by centrality will have a centrality greater than 1 standard deviation (SD) from the mean and a clustering less than 1 SD from the mean. Conversely, the

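### Does the AIM 3 power statement describe a different set of patients from the one the primary steps comparison will analyse?

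*SAP*

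**What the plan says.** Two places in the SAP define who counts as exposed, and they agree. Under AIM 3, Recruitment Goals: "all the patients on that shift are considered exposed to the COACH education". Under AIM 3, Exposure: "all patients regardless of participation in the COACH education will be analyzed as exposed to the intervention via social spread". The Exposure paragraph then forms the two primary-analysis groups from complete shifts, and the Analysis paragraph compares change in steps between them by t-test.

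Recruitment Goals also estimates how many patients COACH could be offered to: "we anticipate approximately half the patients would be eligible for a kidney transplant but not on the list". From 250 participants it derives at least 125 such patients, or roughly 10 per shift.

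The section on sample size and power for AIM 3 uses the same round number under a different label: "We estimate at least 10 patients per shift will be exposed to the intervention either directly through participation in the intervention or indirectly". Six shifts per condition then give 60 per arm, and the section concludes: "With 120 patients (60 patients in each treatment arm) we will be powered to detect a difference of 1 step".

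Two further sentences bear on the set. The AIM 3 eligibility text says: "Patients will be excluded if they are ineligible for a kidney transplant, had a previous kidney transplant, or have an active living donor". It does not say whether this governs selection for COACH or entry to the analysis. The AIM 3 covariate list reads: "Covariates: Age, Marital Status, insurance, transplant eligibility, HD shift, HD Clinic, network attributes".

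**The concern.** The 10 per shift in the power section looks like the count of eligible, unlisted patients carried over from Recruitment Goals, while the t-test takes everyone on the shift. The outcome is position on an eight-step ladder whose first step is suitability for referral and whose seventh is being active on the waiting list. Patients who are ineligible or already listed have little room to advance. If they make up about half of each shift and do not move, a 1-step gain among the others averages to 0.5 step, and the 1-step power claim would not describe the planned test. A whole-shift difference could also be misread as the effect in patients able to progress.

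**Working it through.** **Inputs.** From the SAP's AIM 3 power section: two-sided t-test, alpha 0.05; effect size 1.06 for 2 steps; means 7 (SD 1.5) and 5 (SD 1.7); 15 per arm for 2 steps and 60 per arm for 1 step. From Recruitment Goals: 250 participants, at least 125 of them eligible and unlisted. From Setting: census of 280. From AIM 3 Retention/Attrition: 5% drop-out. Two SDs are carried because the printed figures do not give the same one:

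- 2 / 1.06 = 1.89
- sqrt((1.5² + 1.7²) / 2) = 1.60

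Both are treated as SDs of change, which the SAP does not confirm. Power is from the noncentral t distribution.

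**Head counts.**

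- Whole shifts: 250 / 2 = 125 per arm; the census caps this at 280 / 2 = 140.
- Eligible and unlisted: 125 / 12 shifts = 10.4 per shift; 10 × 6 = 60 per arm.

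**The plan's own figures.** With effect size 1.06, 15 per arm gives 80.0% power for 2 steps. For 1 step the effect size is 1 / 1.89 = 0.53; 80% power needs 57 per arm, and 57 / 0.95 = 60. Power at 60 per arm is 82.1% (SD 1.89) or 92.3% (SD 1.60). The statement is correct for the number it names.

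**Whole shifts, 1-step difference between arms.** At 125 per arm, power is 98.7% (SD 1.89) or 99.8% (SD 1.60).

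**Whole shifts, effect confined to half the patients (illustration).** Let half show exactly zero change. The other half have the SD above, a mean change of m in the lower arm and m + 1 in the upper. The arm difference is 0.5 × 1 = 0.5 step, and the variance in an arm whose movers average μ is 0.5 × SD² + 0.25 × μ². At 125 per arm:

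| m | Power, SD 1.89 | Power, SD 1.60 |
|---|---|---|
| 0 | 81.4% | 91.2% |
| 1 | 71.9% | 81.3% |
| 2 | 56.9% | 63.6% |

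**Partial response in the other half.** If they show a fraction f of the 1-step effect and the SD stays at 1.89, the arm difference is 0.5 + 0.5f:

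- f = 0.25: 0.63 step, 74.2%
- f = 0.38: 0.69 step, 82.1%, the same as 60 per arm
- f = 0.50: 0.75 step, 87.9%

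**The expected 2-step difference, halved to 1 step.** In the zero-change illustration at 125 per arm, the lowest power (m = 2) is 96.8% (SD 1.89) or 98.2% (SD 1.60).

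All figures treat patients as independent, as the SAP's own calculation does.

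**The case for a change.** The strongest case for a change is that the agreement between 10 and 10.4 is unlikely to be chance, so the author probably had eligible, unlisted patients in mind when sizing the study. The SAP never states what effect it expects in everyone else. The direction of the power change is therefore unknown, and someone could settle the set after seeing results. Naming it beforehand would cost little, since chart review of all patients and verification of listing status are already planned.

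Part of this stands. No sentence reconciles the two counts, and the scope of the AIM 3 exclusion is open. But the power section describes its 10 per shift as exposed, directly or indirectly, with 10 as a minimum. Exposed is the term the SAP applies to everyone on a shift. On that reading the set is defined and 60 is a conservative number.

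If the exclusion is instead taken to govern all of AIM 3, 60 per arm is the right number and its 82% stands. That reading fits poorly with the two statements covering all patients, and with eligibility being listed as a covariate. The covariate does not settle the matter, because AIM 2 lists it too. Nor does the intention-to-treat sentence, "In the unlikely event no patients on the shift participate in the COACH education, they will be analyzed as intention to treat", which fits either set.

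The low power figures rest on stacked assumptions: exactly half unable to move, no variation among them, and movers in the lower arm already advancing 2 steps. If the earlier 7 versus 5 came from a mixture of eligible and ineligible patients, the halving does not apply at all.

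**Conclusion.** No change is needed. This is a missing link between two counts, and an analyst can fill it by following the Exposure paragraph. Whole shifts are a sound intention-to-treat set for a hypothesis about spread through a shift's network. Assignment is by shift, so taking everyone on it gives a fair Cluster versus Central comparison on this point.

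The power claim has not been shown to be wrong. It reproduces at 60 per arm (82% or 92%) and rises to about 99% at 125 per arm if a 1-step difference holds across the arm. The fall to 57-81% (SD 1.89) or 64-91% (SD 1.60) is conditional on half the patients showing no change. The documents give only an approximate half, and they do not say that the rest cannot move. The 2-step difference that the SAP expects keeps about 97% power or more even when halved, although it would then be reported as about 1 step.

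Making eligible, unlisted patients the primary set would exchange one defensible question for a narrower one. If it were done for steps alone, the two primary outcomes would be analysed in different patients. It would also give up power if the remaining patients respond at about 38% of the effect or more. A sentence naming the set and its size would help a reader, but the planned comparison does not depend on it. The conclusion rests on treating the printed SDs as SDs of change and on leaving aside clustering by shift, which is a separate question.
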